Participants undergoing SSLF will be randomized to receive either 2 weeks of post-op gabapentin or placebo, starting with 300mg qhs for the first 3 days post-op, then on day 4 patients will dose escalate to 300mg bid for 11 additional days for a total of 2 weeks.

- UNC IDS will provide active and placebo capsules (300mg dose), 1 x 3d postop (subtotal 3), 2 x 11d postop (subtotal 22) = 25 total
- We will use NIH Common Terminology of Criteria for Adverse Events version 4.0 (CTCAE) criteria (15)
- Specific AEs to assess:
 - Dizziness ~ 15%
 - Sedation/somnolence ~ 15%
 - Nystagmus ~ 8% (involuntary movements of the eyeballs)
 - Ataxia ~ 3% (lack of coordination of muscle movements)

Patient incentives

- 6 wk visit - \$50

Data and Safety Management

Study data will be entered into and stored in a secure REDCap database hosted by UNC-CH.

Adverse events will be monitored and assessed using the NIH Common Terminology of Criteria for Adverse Events version 4.0 (CTCAE) criteria, which grades each adverse events from Grade 1 (mild), Grade 2 (moderate), Grade 3 (severe), Grade 4 (life threatening), Grade 5 (death related to AE). (15)

- The PI will be responsible for assessing each AE in terms of whether the AE is expected and/or attributable to the study drug along with the severity of the AE using the CTCAE ratings

- Serious AEs will be reported to the IRB per IRB UPIRSO guidelines
- Specific AEs to assess:
 - Dizziness ~ 15%
 - Sedation/somnolence ~ 15%
 - Nystagmus ~ 8% (involuntary movements of the eyeballs)
 - Ataxia ~ 3% (lack of coordination of muscle movements)

For example, dizziness is rated/described below in the NCI CTCAE(10) Table.

| Nervous system disorders | | | | | |
|--|--|---|--|---|---|
| Adverse Event | Grade | | | | |
| | 1 | 2 | 3 | 4 | 5 |
| Dizziness | Mild unsteadiness or sensation of movement | Moderate unsteadiness or sensation of movement; limiting instrumental ADL | Severe unsteadiness or sensation of movement; limiting self care ADL | - | - |
| Definition: A disorder characterized by a disturbing sensation of lightheadedness, unsteadiness, giddiness, spinning or rocking. | | | | | |

Schedule of Assessments (see Table 1.)

Baseline visit:

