Interested patients will be consented and if eligible, baselined at their surgical consult visit or before their pre-op appointment. Participants who have absolute or relative contraindications to gabapentin will be excluded from participation in the study through inclusion/exclusion criteria. This visit may occur up to 3 months before their surgery. Participants will be screened for cognitive impairment by the Mini-Cognitive Assessment, and those who score 2 or less will be considered screen failures. Participants will also complete a standardized and validated symptom bother (PFIQ-sf7) and QoL questionnaires (PFDI-sf20), as well as the standardized and validated PROMIS pain interference, pain intensity, and global mental and physical health questionnaires.

Source data collected as part of routine clinical care may be used to complete CRFs as long as the window between prior data collection and the baseline visit does not exceed 18 months. This includes previously performed POP-Q exams as well as previously collected questionnaires.

- Informed consent
- Inclusion/Exclusion Form
- Baseline form (Demographics, Medical & Surgical History, pain/analgesic med use, POP-Q exam record)
- Mini-Cognitive Assessment
- PFIQ-sf7, PFDI-sf20, PROMIS questionnaires

Randomization:

The randomization table will be given to IDS who will implement randomization for the study and provide the study drug that will be given to patients before their surgery. Randomization will be done by site – Hillsborough and Rex, in a 1:1 ratio and in blocks of 4.

Surgery:

Surgical data will be collected on a Surgical Procedures Form and include items listed below.

- American Society of Anesthesiologists (ASA) grade
- Concomitant procedures performed
- Estimated blood loss (EBL)
- Intraoperative complications
- Voiding trial results

Follow-Up Procedures:

- Daily for 2 weeks after discharge: Patients will complete a Study Drug-Pain Med Count Form and Surgical Pain Scale ratings every day for the first 2 weeks after discharge.
- 2-3 days after discharge: We will call patients 2-3 days after discharge to assess for any AEs and remind pts to dose escalate. We will use the NIH Common Terminology of Criteria for Adverse Events version 4.0 (CTCAE) to determine AE severity/grade.

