- Week 1 and Week 2 calls: At Week 1 and Week 2 we will call patients to administer the PROMIS questionnaires. We will also remind patients to complete the Study Drug-Pain Med Count Form and Surgical Pain Scale, and will review any potential AEs.
- Week 3, 4, 5: Patients will complete the PROMIS questionnaires, as well as a Pain Med Count Form and Surgical Pain Scale at the end of week 3, 4, and 5 post-operatively.

Week 6 Visit:

Patients will return to clinic for a postoperative visit around week 6, in which all of the assessments listed in the table below will be performed. Patients will again complete the symptom bother (PFIQ-sf7) and QoL questionnaires (PFDI-sf20), as well as the PROMIS pain interference, pain intensity, and global mental and physical health questionnaires. In addition, we will assess for any AEs or post-operative complications that may have occurred since discharge, as well as current pain/analgesic med use.

- Week 6 form (pain/analgesic med use, post-op complications)
- PFIQ-SF7, PFDI-SF20, PROMIS questionnaires
- Surgical Pain Scale

Table 1. Schedule of Assessments

| Schedule of Assessments | # ?s | Baseline | 2-3 day post-op call | Daily for 2 wks post-op (completed at home) | Wk 1 call | Wk 2 call | Every wk Wk 3-5 (completed at home) | 6 Wk visit |
|--|------|----------|----------------------|---|-----------|-----------|-------------------------------------|------------|
| PFDI-20 | 20 | X | | | | | | X |
| PFIQ-7 | 7 | X | | | | | | X |
| PROMIS pain interference/intensity | 7 | X | | | X | X | X | X |
| PROMIS depression/anxiety short forms | 8 | X | | | | | | X |
| PROMIS global mental/physical health | 4 | X | | | X | X | X | X |
| Medical/Surgical history | | X | | | | | | |
| Pain medications assessment | | X | | | | | X | X |
| Study Drug-Pain Med Count Form | | | | X | X | X | | |
| Surgical pain scale (SPS) + gluteal pain | 6 | | | X | X | X | X | X |
| Adverse events assessment | | | X | | X | X | | X |
| Total # of questions at each visit | | 46 | | 6 | 18 | 18 | 18 | 52 |

Outcome measures

Primary Outcome

Overall post-operative pain will be measured by item 2 of the surgical pain scale (SPS) on post-op day 7. This item measures the average pain felt during normal activity in the last 24 hours on a scale of 1-10.

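### Post-operative complications between the end of surgery and discharge fall outside both dated collection windows, and adverse events in that interval rest on telephone recall

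*Combined protocol and SAP*

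**What the plan says.** Dosing is timed from the operation. The Intervention section has study drug "starting with 300mg qhs for the first 3 days post-op". Safety collection is described in several places, with different anchors.

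- **Surgery:** "Surgical data will be collected on a Surgical Procedures Form and include items listed below". The only complications item listed is "Intraoperative complications". The list also contains "Voiding trial results", with no timing given.
- **Follow-Up Procedures, first call:** "We will call patients 2-3 days after discharge to assess for any AEs and remind pts to dose escalate". Table 1 heads the same contact "2-3 day post-op call".
- **Follow-Up Procedures, Week 1 and Week 2 calls:** potential AEs are reviewed, with no look-back period stated.
- **Week 6 Visit, text:** "we will assess for any AEs or post-operative complications that may have occurred since discharge".
- **Week 6 Visit, form list:** "Week 6 form (pain/analgesic med use, post-op complications", with no start date.
- **Table 1:** the AE row is marked at the first call, the Week 1 and Week 2 calls and the 6-week visit. There is no surgery or in-hospital column.

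Data and Safety Management says that AEs will be monitored and graded by CTCAE. It does not say when collection begins.

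**The concern.** Treatment follow-up begins when surgery ends, but the one dated question about post-operative complications begins at discharge. The form completed for surgery stops, for complications, at the operation. Between the two lies the immediate recovery period, in which no assessment is scheduled.

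What is at stake is the completeness of the safety record in a trial with a planned minimum of 38 women. If site staff follow the wording, a complication that arises and resolves before discharge has no clear place to be recorded. An AE in that interval is recorded only if the woman mentions it at a later call. The investigator must then judge its grade and attribution without any planned in-hospital note.

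**Working it through.** The plan gives no figure to reproduce, because the question is one of coverage. The check takes each collection point and asks whether its wording reaches the interval from end of surgery to discharge.

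| Collection point | Period asked about | Complications in the interval | AEs in the interval |
|---|---|---|---|
| Surgical Procedures Form | Operation only, for complications | Not covered | No AE item listed |
| First call | Any AEs, no limit | Not named | Not excluded; by recall |
| Week 1 call | Potential AEs, no limit | Not named | Not excluded; by recall |
| Week 2 call | Potential AEs, no limit | Not named | Not excluded; by recall |
| Week 6 visit text | From discharge | Not covered | Not covered |
| Week 6 form line | Undated | Named, not clearly covered | Not named |

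**Complications.** Two collection points name complications with a stated period. One ends with the operation and the other begins at discharge, so the interval falls between them. The undated form line does not settle the matter. It describes the form for the visit whose own text sets the look-back at discharge, and a reader would naturally take the period from that text. The gap does not depend on an overnight stay, since some time passes between operating room and discharge even on the same day.

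**AEs.** In Follow-Up Procedures, the reference to discharge sets when the first call is made. It does not restrict what is asked. The Week 1 and Week 2 reviews also carry no restriction. All three calls can therefore pick up an event from the hospital stay, but no script or prompt directs the caller to ask about it.

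**Timing of the first call.** The text counts the 2 to 3 days from discharge and Table 1 counts them from surgery. The two agree only if discharge is on the day of surgery. The difference decides how soon in-hospital events are first asked about.

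**Exposure before discharge.** Length of stay is not given. Assuming 0 to 3 nights in hospital and one capsule per night, 0 to 3 of the 25 capsules would be taken before discharge, and 3 / 25 = 12%. This range describes possible exposure. It does not convert to a number of missed events, because the documents give no onset times.

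**The case against.** The strongest reply is that the plan has other routes. Three calls ask about AEs without a time limit, and nothing stops a post-operative complication from being raised as an AE at any of them. Data and Safety Management also commits to AE monitoring and to reporting serious AEs to the IRB, with no discharge limit. This stands for AEs, which are not shut out of the record. For complications it helps only in part, because none of the calls is told to ask about them.

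A second reply is that the surgical form's list is not clearly exhaustive and includes voiding trial results, so it may reach past the operation. That is fair, but a voiding result of unstated timing does not replace a field for post-operative complications.

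A third reply is that the authors use discharge and surgery interchangeably. Table 1 labels as post-operative both the first call and the daily forms that the text counts from discharge. This may reflect a short stay. If so, the week 6 wording is loose rather than intended, and correcting it costs even less.

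Stronger readings are tempting, and the documents do not support them:

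- **Drug AEs from the first in-hospital dose are lost.** The documents do not say where the first capsule is taken. Study drug is handed over before surgery and taken at bedtime, so with same-day discharge no dose need precede discharge.
- **About one in three cases is missed.** At the plan's 15% for dizziness or sedation, 19 women would give 19 × 0.15 = 2.85 expected cases of each. A third of that is 0.95. But the one-third fraction has no source in the documents, and the sum assumes that three open-ended calls recover nothing.
- **The AE comparison is biased towards no difference.** Anaesthetic and narcotic effects can occur in both arms, so leaving out early events could remove shared background instead. AEs are not a listed outcome, and the analysis plan specifies no AE comparison.

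**Conclusion.** The point holds for post-operative complications: as worded, both dated windows leave out the time from end of surgery to discharge, and the undated form line does not clearly fill it. For AEs it holds in a weaker form, since they remain collectable but depend on recall at unscripted calls.

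Its size in events cannot be given, and no direction of bias is shown. The conclusion rests on reading the week 6 sentence literally and on that sentence governing the form for the same visit. It needs no assumption about length of stay. This is a modest gap in the safety record. It does not touch the primary pain comparison.

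**What to change.** Make four changes.

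1. In the Week 6 Visit section, start the look-back for AEs and post-operative complications at surgery instead of discharge, and give the Week 6 form the same start.
2. In Follow-Up Procedures, state that the first call covers AEs since surgery. This adds a look-back where none is stated now.
3. Add to the Surgical Procedures Form a field, abstracted from the chart at discharge, for post-operative complications and AEs that occurred before discharge.
4. Reconcile the Follow-Up Procedures text with the Table 1 heading on whether the first call is counted from discharge or from surgery.

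The cost is some rewording and a few chart-abstracted fields, with no added visit or procedure. Reported AE and complication counts will be slightly higher, because the record will be more complete.

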Randomized controlled trial of gabapentin vs placebo for postoperative pain after sacrospinous ligament fixation for pelvic organ prolapse

NCT number: NCT03123861

Document Date: 03-08-17

Randomized controlled trial of gabapentin versus placebo for postoperative pain after sacrospinous ligament fixation for pelvic organ prolapse

Principal Investigator: [name], University of North Carolina at Chapel Hill

BACKGROUND / RATIONALE

Pelvic organ prolapse (POP), the herniation of the bladder, uterus, or rectum, into and often beyond, the vaginal opening, affects 40% of postmenopausal women, and significantly impairs quality of life.(1) POP is often managed surgically, and currently, one in every eight women will undergo POP surgery during her lifetime.(2)

A commonly performed procedure for POP is a sacrospinous ligament fixation (SSLF), which is a vaginal surgery that involves suspending the vaginal apex to the sacrospinous ligament suspension with sutures. Beyond routine postoperative pain, a SSLF may result in significant gluteal pain as a result of the vaginal sutures affecting/impinging on the sacral nerve roots.(3) Unfortunately, postoperative gluteal pain is not uncommon with 12% of patients reporting significant gluteal pain and 4% having persistent pain 6 weeks after surgery.(4)

In this study, we aim to compare the impact of gabapentin versus placebo on postoperative pain after SSLF. Our rationale is that studies have shown that preoperative gabapentin, a non-opioid analgesic, resulted in a lower narcotic use postoperatively.(5) Decreasing use of standard of care postoperative narcotic pain medications would also decrease adverse events due to narcotics such as nausea, vomiting and constipation, and potentially decrease the long-term risk of opioid dependence. (6, 7) As an additional benefit, a careful assessment of actual opioid will help to inform best practices for prescribing, as it is possible that we are overprescribing narcotic medications for this type of surgery.(6, 8, 9) We propose to evaluate a longer two-week course of gabapentin because we currently use gabapentin to treat neuropathic pain after SSLF; thus, gabapentin may help to address overall pain as well as neuropathic gluteal pain that can occur after SSLF. Furthermore, gabapentin is a relatively safe medication with the primary adverse events being dizziness and sedation.

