(SPS validated by OPTIMAL study and in older women; OPTIMAL was a multicenter NIH sponsored Pelvic Floor Disorders Network study comparing SSLF to uterosacral ligament suspension surgery for POP).(11, 12)

Secondary outcomes:

1. Gluteal pain on post-op day 7 will be measured by a numeric rating scale like that used in the SPS (0-10)
2. Other pain scale items such as SPS pain at rest, pain w/normal activity (primary outcome), unpleasantness of worst pain sensation, gluteal pain at rest and gluteal pain w/normal activity on POD#7
3. Daily Narcotic pain medication use for 2 weeks post-op and then through week 6 post-op

DATA ANALYSIS

Sample size

OPTIMAL study found that SPS score for pain with normal activity

- Wk 2 = mean 2.9 (2.6 SD) median 2 (1-4 IQR) range: 0-10
- Pain is likely to be higher at Wk 1
- 17 per group to detect 2.5 difference in SPS, SD 2.6 with alpha 5%, power 80%
- **If 20% drop out, need 19 per group so 38 total at min**

Statistical Analysis Plan

- Bivariate analyses to compare our two cohorts: Student's t-test, chi-square/Fisher's exact and Mann-Whitney U for continuous variables, categorical variables and ordinal/skewed data respectively.

Primary outcome

- We will compare pain with normal activity scores on POD#7 using Student's t-test or Mann-Whitney U as appropriate

Secondary outcomes

- We will use Student's t-test or Mann-Whitney U as appropriate to compare gluteal pain scores on POD#7
- We will compare total narcotic use in average morphine milliequivalents per day during the first two weeks using Student's t-test or Mann-Whitney U as appropriate
 - Convert different narcotics into morphine equivalents and add up total narcotic use as needed
 - Compare with t-test if parametric vs Mann-Whitney U if nonparametric
 - Perform a linear regression analysis and adjust for baseline pain medication usage in order to account for the fact that baseline pain medication usage may impact postoperative narcotic use. We can also adjust for postoperative non-narcotic pain medication.

References

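### The SPS and gluteal pain items are not asked at baseline, so prior gluteal pain cannot be described and the POD 7 pain analyses cannot adjust for the same item

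*Combined protocol and SAP*

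**What the plan says.** Table 1 has a row for "Surgical pain scale (SPS) + gluteal pain", which in full reads "Surgical pain scale (SPS) + gluteal pain | 6 | | | X | X | X | X | X". The first two cells after the item count, Baseline and the 2-3 day call, are empty. The daily diary, the week 1 and week 2 calls, weeks 3 to 5 and week 6 are marked. The totals row reads "Total # of questions at each visit | | 46 | | 6 | 18 | 18 | 18 | 52".

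The bulleted list for the baseline visit names "PFIQ-sf7, PFDI-sf20, PROMIS questionnaires" and a baseline form covering demographics, history, pain and analgesic medication use, and the POP-Q record. It names no SPS or gluteal rating. The one pain measure scheduled at baseline is in the row beginning "PROMIS pain interference/intensity | 7 | X".

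The primary outcome is SPS item 2 on POD 7, and the first secondary outcome is a 0-10 gluteal pain rating on the same day. The Statistical Analysis Plan compares each by an unadjusted t-test or Mann-Whitney U test. The only baseline adjustment it plans is for pain medication use, and that is listed under the narcotic-use outcome. No exclusion criterion concerns existing gluteal pain.

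**The concern.** Gluteal pain is the reason this operation was chosen for study. The Background attributes it to the sutures and cites "12% of patients reporting significant gluteal pain and 4% having persistent pain 6 weeks after surgery". A reader of the results will want to know how much of the gluteal pain reported on POD 7 or at week 6 is new. With no gluteal rating before surgery, the trial cannot say.

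Two further losses follow. In a trial of 38, the arms may differ by chance in pain before surgery, and this could not be examined on the scale of either outcome. Nor could the POD 7 analyses use the baseline value of the same item to reduce residual variance. The SAP already accepts that reasoning for narcotic use, where it adjusts for baseline medication because of its likely influence on later use.

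**Working it through.** **1. Is the blank cell real?** Add the item counts in Table 1.
- Baseline without the row: PFDI 20 + PFIQ 7 + PROMIS pain 7 + PROMIS depression/anxiety 8 + PROMIS global 4 = 46, the stated baseline total.
- Week 6 with the row: 46 + 6 = 52, the stated week 6 total.

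The six items are counted at week 6 and not at baseline, so the blank is not an artefact of how the table was read.

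**2. Reproduce the plan's sample size.** Inputs from the Sample size section: difference 2.5, SD 2.6, alpha 5% (two-sided assumed, as sidedness is not stated), power 80%.

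n per group = 2 × (1.960 + 0.842)² × (2.6/2.5)² = 16.98, so 17. This matches. Using the t distribution gives 17.99, so 18.

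**3. Number evaluable.** 19 per group with the plan's 20% dropout leaves 19 × 0.8 = 15.2, about 15 per group.

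**4. Effect of a baseline covariate on the primary outcome.** Residual SD = 2.6 × √(1 − r²), where r is the correlation between baseline and POD 7 scores. The documents give no r, so a range is assumed. Power is for a difference of 2.5 by a two-sided t-test.

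| r (assumed) | Residual SD | Power, 15 per group | Power, 17 per group |
|---|---|---|---|
| none | 2.60 | 72.0% | 77.6% |
| 0.1 | 2.59 | 72.4% | 78.0% |
| 0.2 | 2.55 | 73.7% | 79.2% |
| 0.3 | 2.48 | 76.0% | 81.3% |
| 0.5 | 2.25 | 83.5% | 88.1% |

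Charging one degree of freedom for the covariate lowers the adjusted figures by about 0.1 percentage point.

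**5. Gain over the PROMIS pain score.** Illustration only: suppose baseline PROMIS pain and baseline SPS item 2 each correlate 0.3 with the outcome and 0.6 with each other.
- PROMIS alone: R² = 0.3² = 0.09, power 76.0% at 15 per group.
- Both: R² = (0.09 + 0.09 − 2 × 0.3 × 0.3 × 0.6)/(1 − 0.36) = 0.072/0.64 = 0.1125. Residual SD = 2.6 × √0.8875 = 2.45, power 77.0%.

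The added gain is about 1 percentage point.

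**6. Chance imbalance.** With 19 per group, the difference in baseline means has a standard error of √(2/19) = 0.32 SD. The normal approximation gives a 12% chance of a difference above 0.5 SD. This would hold for any baseline variable. Here it could not be seen.

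**The case against.** The strongest reply is that no planned analysis needs this baseline. The aim is a between-arm difference in POD 7 scores. Randomisation balances prior pain in expectation, and the unadjusted test's error rate already allows for chance imbalance. This stands, and three stronger readings that a reader might infer are not supported:

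- **That the gluteal comparison is biased.** It is not. Allocation is randomised 1:1 by site.
- **That the secondary aim concerns pain caused by the procedure.** The Study Aims section states it as gluteal postoperative pain on POD 7. The link to the sutures is rationale, not the definition of the outcome.
- **That patients with prior gluteal pain could outnumber the true cases.** The documents give no prevalence before surgery. The 12% refers to significant pain without a POD 7 time point, and the outcome is a 0-10 score, not a count of cases.

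It can also be said that PROMIS pain is collected at baseline and could serve as covariate. For the primary outcome this is largely fair, and the correlation with SPS item 2 may be low anyway: the item covers 24 hours, the baseline visit may be up to 3 months before surgery, and POD 7 follows an operation. But the SAP plans no PROMIS adjustment, and the documents describe no gluteal item in that measure. Questionnaires collected up to 18 months before the baseline visit are also accepted, so a score could be 18 + 3 = 21 months old at surgery.

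Finally, the content of the baseline form is not shown. The supportable statement is that no gluteal item is named at baseline, not that none can exist.

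**Conclusion.** The gap is real but minor. The schedule, its totals and the baseline visit list agree that the SPS and gluteal items are not taken before surgery. The validity of the randomised comparison is unaffected. What is lost is the ability to describe prior gluteal pain and separate it from new pain, the ability to check balance on the outcome's own scale, and some precision. The first two losses do not depend on any assumed figure and matter most for the gluteal outcome.

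The precision loss on the primary outcome rests on an assumed correlation: negligible at 0.2 or below, about 4 percentage points of power at 0.3 and 11 to 12 at 0.5, with 15 per group. It shrinks if baseline PROMIS pain is used instead, to about 1 point under the illustrative correlations above.

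**What to change.** In Table 1, add an X in the Baseline column of the SPS and gluteal pain row and change the baseline total from 46 to 52. Add the same items to the baseline visit list. In the Statistical Analysis Plan, prespecify the baseline value of the same item as covariate in the POD 7 analyses of SPS item 2 and of gluteal pain, for example by linear regression on treatment and baseline score. Report the baseline gluteal scores by arm.

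The cost is six more questions at an existing visit, a load already accepted at week 6, and one covariate in each of two analyses. Patients already past the baseline visit will have no value, so if recruitment has begun the SAP should also say how they enter the adjusted analysis.

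### The primary POD#7 comparison leaves out the randomisation stratum (site) and the scheduled baseline PROMIS pain score: a valid test, but a pre-specified site term is nearly free and baseline pain may add precision

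*Combined protocol and SAP*

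**What the plan says.** All references are to the combined protocol and SAP.

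- **Statistical Analysis Plan, Primary outcome:** "We will compare pain with normal activity scores on POD#7 using Student's t-test or Mann-Whitney U as appropriate". There is no site term and no covariate. The only adjusted model in the plan is a linear regression for narcotic use, a secondary outcome, with baseline pain medication as covariate.
- **Randomization:** "Randomization will be done by site", at two sites, 1:1, in blocks of 4.
- **Table 1:** a baseline pain measure is scheduled ("PROMIS pain interference/intensity | 7 | X", the X being the baseline column). The outcome scale is not: its row reads "Surgical pain scale (SPS) + gluteal pain | 6 | | | X", with the baseline cell empty.
- **Baseline visit:** "This visit may occur up to 3 months before their surgery". Routine-care data may be used on the case report forms "as long as the window between prior data collection and the baseline visit does not exceed 18 months", and "This includes previously performed POP-Q exams as well as previously collected questionnaires".
- **Sample size:** "17 per group to detect 2.5 difference in SPS, SD 2.6 with alpha 5%, power 80" per cent, then 19 per group to allow for 20% dropout.

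**The concern.** A design that stratifies by site treats site as possibly prognostic. An analysis that ignores the stratum leaves any between-site variation in the error term, so the standard error is too large when sites differ and the test falls below its nominal level. Baseline pain is a natural second covariate, and the plan already accepts baseline adjustment for narcotic use.

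The trial is small. If 20% of 38 are lost, 38 × 0.8 = 30.4, or about 15 per arm, remain. At that size residual variance largely decides whether a 2.5-point difference can be detected, and both covariates are already scheduled. A single pre-specified model would also settle the choice between t-test and Mann-Whitney, which the plan leaves open.

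**Working it through.** **Inputs from the documents.** Difference 2.5, SD 2.6, alpha 5%, target power 80%, 17 per group, 19 per group enrolled, 20% dropout (Sample size); two sites, 1:1, blocks of 4 (Randomization).

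**Assumptions, because the documents give no value.** Correlation r between baseline PROMIS pain and POD#7 SPS item 2, from 0 to 0.5; site difference of 0 to 2 points; equal split between sites unless stated.

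**1. The plan's figure.** n = 2(σ/δ)²(z₀.₉₇₅ + z₀.₈₀)² = 2 × (2.6/2.5)² × (1.960 + 0.842)² = 16.98, so 17 per group. This reproduces with a two-sided normal approximation. The noncentral t needs 18; 17 per group has 77.6% power.

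**2. Formula for adjusted power.** Power = P(|T| > critical t), where T is noncentral t with λ = δ / √[2σ²(1 − r²)f / n]. The factor f is the variance cost of chance covariate imbalance.

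**3. Unadjusted, 15 per arm.** df = 28, critical t = 2.048, λ = 2.5/√(2 × 6.76/15) = 2.633. Power is 72.0%. At 19 per arm it is 82.2%.

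**4. Site alone, 15 per arm.**
- Sites alike and balanced by blocking: df = 27, critical t = 2.052, λ unchanged. Power is 71.9%, a loss of 0.1 points. Simulation with blocks of 4 within site gave losses of up to 0.3, and about 0.5 when 8 of 38 were removed at random.
- Sites differing by 1 point within a total SD of 2.6: within-site variance = 6.76 − 0.25 = 6.51, λ = 2.683, power 73.5%. Simulation gave 73.1% against 71.9% for the t-test.

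**5. Site plus baseline PROMIS, 15 per arm, no site difference.** df = 26, critical t = 2.056. Take f = 1 + 1/26 = 1.038 if blocking balances site, and f = 1 + 2/25 = 1.08 if both covariates are imbalanced by chance.

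| r | Site balanced | Both imbalanced |
|---|---|---|
| 0 | 70.1% | 68.4% |
| 0.1 | 70.5% | 68.9% |
| 0.2 | 71.9% | 70.2% |
| 0.3 | 74.1% | 72.5% |
| 0.4 | 77.5% | 75.8% |
| 0.5 | 81.9% | 80.4% |

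Against 72.0%, break-even r is 0.21 in the first column and 0.28 in the second. Simulation gave 70.1%, 74.4% and 81.9% at r = 0, 0.3 and 0.5, which supports the first column. At 19 per arm with f = 1 + 1/34, power is 81.0% at r = 0, 84.5% at 0.3 and 90.6% at 0.5, against 82.2%.

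**6. Type I error** (simulation, r = 0.3, 100,000 replicates per setting). For site differences of 0, 0.5, 1 and 2 points the t-test gives 4.9%, 5.0%, 4.6% and 3.5%. The adjusted model stays at 4.9–5.1%.

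**7. Older baseline answers.** If r would be 0.3 for fresh answers and the stability of the score over time is 0.5, r becomes 0.3 × 0.5 = 0.15. Adjusted power is then 71.1% by the formula (70.5% by simulation), below the unadjusted test.

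**8. Missing baseline values.** With 3 of 30 missing at r = 0.3, overall-mean imputation gives 73% and dropping those participants gives 68%, against 72% unadjusted. Type I error with imputation is 4.9–5.1%.

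**9. Bounded, skewed scores.** Integer 0–10 scores were fitted to the week 2 mean, SD, median and IQR in Sample size, with the other arm shifted by 2.5 and no site effect. The t-test has 63% power. Site plus baseline has 61% at r = 0, 62% at 0.19, 65% at 0.28 and 72% at 0.47. A site-stratified rank test (van Elteren) has 59%, and a separate fit to the same summaries gave about 60% for Mann-Whitney. Type I error was 4.8–5.1%.

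**The case against.** The strongest reply is that nothing is broken. The planned test is valid, no figure in the plan is contradicted, and replacing a valid primary test is partly a matter of preference. The two covariates also differ. Site is worth about 1 power point, and only if the sites differ. Every larger gain comes from an assumed correlation that the documents do not supply, and there are reasons for it to be low: PROMIS is a different instrument, it measures pain before surgery, the visit may be 3 months earlier, and older answers may be reused. All of this stands. It is why the site term is the core of the recommendation and baseline PROMIS is conditional.

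Several stronger readings are tempting and are not supported:

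- **That the unadjusted comparison is biased or anti-conservative because it ignores the stratum.** With 1:1 blocks within site it is neither; a 1-point site difference takes its type I error only to 4.6%.
- **That adjustment will raise power.** The sign of the PROMIS effect is unknown below r of about 0.2 to 0.28.
- **That a stratified rank test recovers power.** In the bounded-score check it had 59%, no better than Mann-Whitney.
- **That the same model should be applied to gluteal pain.** No calculation supports this. The Background reports significant gluteal pain in only 12%, about 2 of 15 per arm, so scores may cluster near zero.
- **That the baseline scores will be 18 months old.** Reuse is permitted, not required; participants are expected to complete PROMIS at baseline, and nothing says it is collected in routine care.

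**Conclusion.** The point holds as an efficiency and pre-specification improvement, not as an error. The site term is close to no-regret: about 0.1 to 0.5 power points lost if sites are alike, about 1 gained at an assumed 1-point site difference, and type I error back to about 5% when sites differ.

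Baseline PROMIS pain is a reasonable but uncertain addition. At 15 per arm, the model with both covariates loses 1.9 points (72.0 − 70.1), and up to 3.6 (72.0 − 68.4), if PROMIS is uninformative. With site balanced it gains 2.1 points at r = 0.3 and 9.9 at r = 0.5; with both covariates imbalanced, 0.5 and 8.4.

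These sizes rest on the plan's difference and SD, two-sided 5% testing and random loss to follow-up. The correlations, site differences, site split and missing rates are assumptions. Confidence is medium, because the documents give neither a correlation nor a site effect.

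**What to change.** Before unblinding, amend the Statistical Analysis Plan as follows.

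1. Replace the primary test with one pre-specified linear model of POD#7 SPS item 2 on treatment and site, reporting the adjusted mean difference with its 95% CI.
2. Pre-specify baseline PROMIS pain as a continuous covariate in that model, with the possible loss stated. If the team does not expect a correlation above about 0.2 to 0.28, keep site alone. Decide this before any outcome is seen by arm.
3. Name the PROMIS score in advance, since Table 1 combines interference and intensity in one 7-item row. Ask those items at the baseline visit, where Table 1 already lists them, and do not reuse older answers for this covariate.
4. Impute a missing baseline value by a treatment-blind rule, such as the overall mean, so that everyone with a POD#7 score is analysed.
5. A site-stratified rank test may be kept as a sensitivity analysis for skewed scores, with no power gain claimed. Leave the gluteal pain analysis as planned.

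The cost is SAP wording, one degree of freedom for site and one more for baseline pain, and the power loss given above if PROMIS proves uninformative. Participants whose older PROMIS answers would have been reused answer the 7 items already scheduled for that visit.
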